Study Endpoints	
The adult and pediatric populations will be combined for primary analysis. Separate secondary analyses also will be performed for the adult and pediatric cohorts. CGM metric analyses will be analyzed separately for the challenge days and subsequent nights and not included in the overall analyses.
 
Primary Safety Endpoints:
 
 
• Severe hypoglycemia (with cognitive impairment such that assistance of another individual is needed for treatment) during study compared with data on severe hypoglycemic events reported by T1D Exchange clinic registry over a 3-month time period.
 
• Diabetic ketoacidosis
 
• Unanticipated adverse device effects
 
• Other serious adverse events
 
• Adverse drug reactions
 
 
Secondary Safety Endpoints:
 
 
• All adverse events (including infusion site reactions)
 
• CGM hypoglycemia outcomes (compared with baseline run-in data and separately when possible with 4 weeks of pre-study CGM data collected at enrollment) 
 
◆ Overall % time <54 mg/dL
 
◆ Postprandial % time <54 mg/dL (30 min, ≤1, ≤2, ≤4, >1 to ≤2 and >2 to ≤4hr)
 
◆ Overall and postprandial % time <70 mg/dL
 
◆ Rate of hypoglycemia events defined as 15 or more consecutive minutes <54 mg/dL
 
 
 
 
Exploratory:
 
 
• Postprandial incremental area under the glucose curve (4 hr)
 
• Peak postprandial glucose
 
• Times in ranges-overall and postprandial (70-180 mg/dL, >180 mg/dL, >250 mg/dL, 70-140 mg/dL)
 
• Mean glucose
 
• Rate of hyperglycemia events, defined as 90 or more minutes >300 mg/dL within 120 minutes
 

PARTICIPANT AREA	DESCRIPTION
	
 
• Overall variability (CV and SD)
 
• HbA1c change from baseline
 
• Patient-reported outcomes
 
 
Exercise and Meal Challenges:
 
 
• Endpoints will be CGM metrics and safety outcomes as indicated above
 
• Separate analyses conducted for the overnight following the challenge
 

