#### Exploratory Endpoints

960

- 961 • Postprandial incremental area under the glucose curve (4 hr)
- 962 • Peak postprandial glucose
- 963 • Times in ranges-overall and postprandial (70-180 mg/dL, >180 mg/dL, >250 mg/dL, 70-140  
964 mg/dL)
- 965 • Mean glucose
- 966 • Rate of hyperglycemia events, defined as 90 or more minutes >300 mg/dL within 120 minutes
- 967 • Overall variability (CV and SD)
- 968 • HbA1c change from baseline
- 969 • CGM metrics for hypoglycemia, hyperglycemia, and variability during daytime and nighttime

970 Patient-Reported Outcomes

- 971 • TRIM-D
- 972 • Trim-DD
- 973 • ITSQ

974 **8.5 Analysis Datasets**

975 For the main analyses, adult and pediatric participants will be pooled. Secondly separate analyses will  
976 be conducted for adults (>18 years) and pediatric (<18 years) participants. Further exploratory analyses  
977 will be conducted within pediatric subgroups.

978 All participants who initiate the Treatment Period and use the study device with the study drug will be  
979 included in the safety analyses.

980 For inclusion in the analysis of CGM metrics, participants must have at least 24 hours of CGM data  
981 during the Treatment Period.

982 **8.6 Statistical Methods**

983 **8.6.1 Analysis of the Safety Event Endpoints**

984 Safety events (ie, not including CGM defined events) will be tabulated for each type of event as the  
985 number of events per participant, the number of participants with > 1 event, and the rate of events per  
986 100 person-years.

987 Since study eligibility excluded participants with 2 or more severe hypoglycemia or DKA events in the  
988 prior 6 months, an unbiased comparison of the event rate during the Treatment Period with the pre-study  
989 event rate is not possible. Therefore, the severe hypoglycemia and DKA event rates will be compared  
990 with the T1D Exchange data, which reported the frequency of 1 or more severe hypoglycemia and DKA  
991 events in the prior 3 months according to age group; this will allow for age-matching with this trial. The  
992 proportion of participants with events during the Treatment Period will be compared with the T1D  
993 Exchange frequency using Barnard's exact test. Study endpoint will be met if severe hypoglycemia and  
994 DKA event rates are not significantly higher during follow-up compared with T1D Exchange frequency.

995 **8.6.2 Analysis of CGM Endpoints**

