15 ketoacidosis (DKA) event rates will be compared with previously published data from the T1D  
16 Exchange registry, which reported the frequency of 1 or more severe hypoglycemia and DKA  
17 events in the prior 3 months according to age group (Table 1 in Section 15). The following two  
18 hypotheses will be tested:

19 Severe Hypoglycemia:

- 20 • *Null Hypothesis:* There is no difference in the proportion of study participants who  
21 experience a severe hypoglycemic event while using Lyumjev with Control-IQ  
22 technology compared with those in the T1D Exchange registry matched by age cohort.  
23 • *Alternative Hypothesis:* There is a nonzero difference in the proportion of study  
24 participants who experience a severe hypoglycemic event while using Lyumjev with  
25 Control-IQ technology compared with those in the T1D Exchange registry matched by  
26 age cohort.

27 Diabetic Ketoacidosis:

- 28 • *Null Hypothesis:* There is no difference in the proportion of study participants who  
29 experience a diabetic ketoacidosis event while using Lyumjev with Control-IQ  
30 technology compared with those in the T1D Exchange registry matched by age cohort.  
31 • *Alternative Hypothesis:* There is a nonzero difference in the proportion of study  
32 participants who experience a diabetic ketoacidosis event while using Lyumjev with  
33 Control-IQ technology compared with those in the T1D Exchange registry matched by  
34 age cohort.

35

36

37

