## 105 **6 Calculation of Endpoints**

### 106 **6.1 Safety Endpoints**

107 An event is defined as a severe hypoglycemic event if the event required assistance of another  
108 person due to altered consciousness, and required another person to actively administer  
109 carbohydrate, glucagon, or other resuscitative actions.

110 An event is classified as a DKA event if the following occur:

- 111 • Symptoms such as polyuria, polydipsia, nausea, or vomiting;
- 112 • Serum ketones >1.5 mmol/L or large/moderate urine ketones;
- 113 • Either arterial blood pH <7.24 or serum bicarbonate (or CO2) <15; and
- 114 • Treatment provided at a health care facility

115

116 For each of the endpoints listed in Section 5.1, the total number of events for each participant  
117 and the event rate per 100 person years will be calculated. Event rates will be calculated as the  
118 total number of events occurring after the start of the treatment period divided by the number of  
119 person years the participant was active in the study. The person years will be calculated as the  
120 number of days between the start of treatment period and either the 13-week visit date or drop  
121 out date divided by 365.25.

122 The proportion of participants with at least 1 or more severe hypoglycemia and DKA events will  
123 be compared with published T1D Exchange data matched by age group (<18 years and ≥18  
124 years) (Table 1). An overall proportion will also be compared with the expected proportions  
125 from the T1D Exchange population using weights derived from the age groups. Study endpoint  
126 will be met if severe hypoglycemia and DKA event rates are not significantly higher during  
127 follow-up compared with T1D Exchange frequency.

128 A sensitivity analyses will restrict to severe hypoglycemic events occurring during the treatment  
129 period which resulted in a seizure or loss of consciousness, and DKA events which resulted in  
130 inpatient hospitalization or prolongation of existing hospitalization.

131 Adverse events occurring in the treatment phase during periods where Humalog is used will be  
132 reported separately.

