## 274 **8 Statistical Analyses**

### 275 **8.1 Key Safety Analyses**

276 The total number of events, number and proportion of participants who experienced at least one  
277 event during the treatment period and the rate of events per 100 person years will be tabulated  
278 for each outcome listed in Section 5.1. The proportion of SH and DKA events will be compared  
279 to proportions of events occurring in a similar time frame among participants enrolled in the T1D  
280 exchange. These proportions have been previously published [2].

281 Barnard's exact test will be used to test the difference in proportions. A two-sided p-value testing  
282 the null hypothesis of no difference in proportions will be reported. For unanticipated adverse  
283 device effects, adverse drug reactions, and serious adverse events, the total number, number and  
284 proportion of participants who experienced at least one event during the treatment period and the  
285 rate of events per 100 person years will be tabulated.

286 All analyses described in this section will be repeated restricting to only severe hypoglycemic  
287 events that were associated with a seizure or loss of consciousness. Summary statistics will be  
288 reported for key safety outcomes by age group (6-13, 14-17, 18-25, 26-49,  $\geq 50$ ).

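### The safety endpoint is met by a non-significant difference from the registry, with no alpha, margin or confidence limit to say what excess of severe hypoglycemia or DKA has been ruled out

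*SAP*

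**What the plan says.** SAP 6.1 states that the study endpoint "will be met if severe hypoglycemia and DKA event rates are not significantly higher during" follow-up than in the registry. Protocol 8.6.1 carries the same rule: "DKA event rates are not significantly higher during follow-up compared with T1D Exchange frequency".

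SAP 3 sets the null for each event as equality ("There is no difference in the proportion of study participants who" have an event, against the age-matched registry), with a two-sided alternative. SAP 8.1 names the test: "Barnard's exact test will be used to test the difference in proportions. A two-sided p-value testing" equality is to be reported.

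The comparison is made under 18 and at 18 and over, and SAP 6.1 adds a pooled version: "An overall proportion will also be compared with the expected proportions", weighted by age group. The protocol makes the pooled population the main one, in the Protocol Summary ("The adult and pediatric populations will be combined for primary analysis") and in section 8.5 ("For the main analyses, adult and pediatric participants will be pooled").

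Four things are absent for these two events:
- a significance level (the 0.05 in SAP 13 is a false discovery rate for the other endpoints);
- a margin;
- a confidence interval (95% intervals are planned for the model-based outcomes and the subgroups only);
- the test statistic and nuisance-parameter search for Barnard's test.

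Protocol 8.3 and SAP 4 justify 160 completers by precision and say that the number has no statistical derivation.

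**The concern.** A test of equality that fails to reject shows only that the data are compatible with equality. They may be equally compatible with a material excess, and the smaller the trial, the larger the excess that passes. A rule that turns non-significance into success needs something to bound that excess, and this one has nothing.

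This is the only success statement in either document, it concerns the two main safety events, and the study is meant to support labeling. A reader told that the endpoint was met cannot tell from that word what increase in risk has been excluded. The sample size is defended on precision, yet no interval is planned that would show the precision for these events.

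**Working it through.** The plan gives no power or margin calculation to reproduce, so the check asks what the written rule lets through.

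**Inputs.** SAP Table 1, Overall rows, summed over age bands:
- Under 18: severe hypoglycemia (62 + 155)/(1,313 + 3,183) = 217/4,496 = 4.83%; DKA (31 + 113)/4,496 = 144/4,496 = 3.20%.
- 18 and over: severe hypoglycemia (138 + 157 + 189)/(2,445 + 2,143 + 1,976) = 484/6,564 = 7.37%; DKA (96 + 43 + 22)/6,564 = 161/6,564 = 2.45%.

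**Assumptions.** Two-sided 0.05. n = 160, with 100 under 18 and 60 adults (80 aged 6-13 plus the minimum of 20 aged 14-17). The two events are independent. Trial and registry definitions are identical. The SAP does not say how the age weights enter the test, so they are entered as synthetic registry counts.

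**Age-weighted references.**
- Severe hypoglycemia: (100 × 217/4,496 + 60 × 484/6,564)/160 = (4.827 + 4.424)/160 = 5.78%, entered as 639 of 11,060.
- DKA: (100 × 144/4,496 + 60 × 161/6,564)/160 = (3.203 + 1.472)/160 = 2.92%, entered as 323 of 11,060.

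**Largest count that still passes.** Two-sided Barnard test, pooled-variance statistic. The narrow search takes the nuisance parameter from 0.8 to 1.25 times the reference; the whole-range search takes it from near 0 to near 1. Limits are Clopper-Pearson. The excess is the limit minus the reference, taken as fixed.

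| Event, search | Last pass (p) | First fail (p) | Ratio at last pass | 95% upper limit | Excess not ruled out |
|---|---|---|---|---|---|
| Severe hypoglycemia, narrow | 15/160 (0.054) | 16 (0.024) | 1.62 | 15.0% | 9.2 points |
| DKA, narrow | 8/160 (0.131) | 9 (0.045) | 1.71 | 9.6% | 6.7 points |
| Severe hypoglycemia, whole range | 17/160 (0.063) | 18 (0.045) | 1.84 | 16.5% | 10.7 points |
| DKA, whole range | 10/160 (0.063) | 11 (0.045) | 2.14 | 11.2% | 8.3 points |

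At the whole-range limits, the 95% interval for the excess starts above zero (+0.5 and +0.1 points). The endpoint could then be declared met although the interval excludes equality.

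**Chance of passing.** P(pass) = binomial CDF at the limit, with n = 160 and p = multiple × reference; joint = product. Narrow search first, whole-range in brackets.

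| True risk | Severe hypoglycemia | DKA | Both |
|---|---|---|---|
| Registry × 1.5 | 69% (85%) | 73% (91%) | 50% (77%) |
| Registry × 2 | 23% (41%) | 41% (67%) | 9% (28%) |

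With no excess, both pass 93% (99%) of the time.

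**Sensitivity.**
- Age splits 110/50 and 120/40: joint pass at 1.5-fold 52% to 54% (82% to 84%).
- n = 200 (125/75), the most who may start treatment: limits 18 and 10 (20 and 12); joint pass 46% (71%) at 1.5-fold and 6% (18%) at 2-fold.
- Pump row (references 4.56% and 1.95%): limits 12 and 6 (14 and 8); joint pass at 1.5-fold 57% (82%).
- CGM-user row (3.86% and 1.15%): limits 11 and 4 under both searches; joint pass at 1.5-fold 67%.

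**The case against.** Several defences have force.

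- **The trial is descriptive.** Protocol 8.2 disclaims formal testing, but only for efficacy. SAP 3 states formal safety hypotheses and both documents state a pass rule, so this does not answer the point.
- **Suspension triggers protect participants.** Protocol 6.6.2 suspends closed-loop use for a root cause analysis at 5 cases of severe hypoglycemia or 5 serious hyperglycemic or ketotic events, and the pediatric cohort at 3. These act well below the pass limits. They are a separate safeguard: they do not enter the success rule or define what a met endpoint excludes.
- **The test is not powerless.** This stands. A tripled risk of severe hypoglycemia would pass only about 0.3% to 1% of the time. A reader might infer that any excess gets through, and the figures do not support that. The weakness lies at 1.5- to 2-fold, chiefly for DKA.
- **The analysis set and reference row can be inferred.** Largely right. The protocol names the pooled population, SAP 1 declares consistency with the protocol, and age is the only matching variable, which points to the Overall row. Saying so in SAP 6.1 is a matter of drafting.
- **Readers can compute intervals from the tabulated counts.** They can, but the stated conclusion would still rest on non-significance.
- **The trial's definitions are broader, so the rule is conservative.** This holds for severe hypoglycemia only. SAP 6.1 counts events needing another person's help for altered consciousness, whereas footnote a of Table 1 requires seizure or loss of consciousness. It is tempting to extend this to DKA, but the documents do not support that. The registry required a doctor's diagnosis and an overnight stay (footnote b). The trial requires no overnight stay but does require symptoms, ketones, a pH or bicarbonate criterion and facility treatment, so the direction is unknown. The pH criterion also differs between SAP 6.1 (arterial below 7.24) and Protocol 6.2.4 (arterial below 7.30 or venous below 7.24), and the two need reconciling.

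**Conclusion.** The concern holds. Both documents let a non-significant difference stand as evidence of safety, and nothing in the rule bounds the excess that passes. That follows from the text and depends on none of the assumptions.

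The size is illustrative. On the Overall row with 160 participants, observed risks up to 1.62 times (severe hypoglycemia) and 1.71 times (DKA) the registry pass, or 1.84 and 2.14 times with a whole-range search. A true 1.5-fold risk of both events passes about 50% (77%) of the time, and a doubling about 9% (28%). The figures rest on the assumed 0.05 level, age split, independence, identical definitions and synthetic registry counts. Across the age splits examined, the 1.5-fold figure reaches 84%.

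A reader might take 50% to 77% as the chance that the planned main analysis passes a 1.5-fold excess. The documents do not support that. The broader severe hypoglycemia definition makes the main analysis harder to pass, so for that event the figures fit the analysis restricted to seizure or loss of consciousness better. Nor is the spread due only to how Barnard's test is computed: age split and registry row move it too.

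**What to change.** 1. In SAP 3, 6.1 and 8.1, report for each event the Clopper-Pearson 95% interval for the trial proportion, and that interval minus the age-weighted Overall registry proportion taken as fixed. Registry sampling error (standard errors 0.23 and 0.18 points) moves these limits by at most about 0.1 point. Make the pooled comparison the main one, as the protocol does, with under 18 and 18 and over as secondary and the Pump and CGM-user rows as sensitivity.
2. Do the same for the restricted analysis (seizure or loss of consciousness; DKA with inpatient care).
3. Still report the prespecified Barnard result and whether the protocol's endpoint was met, stating the alpha, test statistic and nuisance search. Do not read non-significance as showing safety. Limit the safety conclusion to the excess that the upper limit rules out.
4. Add no new margin. SAP version 4.0 is dated after follow-up was complete, so label the change post hoc in the version history.
5. Either amend Protocol 8.6.1 to match, which needs IRB approval under Protocol 10.2, or record the departure in SAP 1. Changing the SAP silently would leave the two documents in conflict.

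Example: 9/160 with severe hypoglycemia is 5.6% (95% interval 2.6% to 10.4%). Subtracting 5.78% gives -3.2 to +4.6 points, so the report would say that an excess above 4.6 points is ruled out.

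The cost is one added table and some wording, with no new participants or data. What is lost is the simple pass/fail message: a met endpoint alone would no longer carry the safety conclusion.

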## 133 **6.2 CGM Endpoints**

134 CGM metrics will be computed for three study periods: (1) Pre-study period, (2) Lead-in period,  
135 and (3) Treatment period. Metrics will be calculated over 24 hours, during the daytime (6:00 AM  
136 to 11:59 PM) and nighttime (12:00 AM to 5:59 AM) periods, and during postprandial periods.  
137 CGM data from periods during the treatment phase where Humalog is used will not be included  
138 in the calculation of CGM metrics.

139 CGM metrics during pre-study period will be computed when possible using 28 days of pre-  
140 study CGM data collected at enrollment. CGM metrics for the lead-in period will be calculated  
141 by pooling all CGM data collected in the last 16 days of the lead in period. If multiple lead-in  
142 periods were required, CGM metrics will only be computed for the most recent. Data collected  
143 from the start of the treatment period until the date of the 13-week visit will be used to calculate  
144 CGM metrics during the treatment period. For those who miss the 13-week visit, data collected  
145 from the start of the treatment period to the last date that data is available or 91 days after the  
146 start of the treatment period, whichever comes first, will be used to compute CGM metrics. At  
147 least 24 hours of CGM data during overall, daytime, nighttime, and postprandial periods must be  
148 available for metrics to be calculated during those periods. CGM metrics will not include  
149 daytime and following nighttime CGM readings on days with meal or exercise challenges; these  
150 will be analyzed separately as described in Section 8.4.

### 151 **6.2.1 Details for Postprandial Periods Not Associated with Meal Challenges**

152 The start time of a meal is defined as the time a carbohydrate is entered into the study pump.  
153 CGM data collected in the 4 hours following the start of the meal will be used to compute

154 postprandial CGM metrics. If another carbohydrate is entered less than 4 hours after the carb  
155 entry, then data collected up until the following carb entry will be used to compute CGM  
156 metrics. Meals are defined as the 3 largest carb entries on a calendar day. All postprandial CGM  
157 data will be pooled for each participant when calculating CGM metrics, and metrics will be  
158 calculated separately for the lead-in and treatment periods.

159 Postprandial % time <54 mg/dL and % time <70 mg/dL will be computed using all postprandial  
160 data and data  $\leq 1$ ,  $\leq 2$ ,  $> 1$  to  $\leq 2$ , and  $> 2$  to  $\leq 4$  hours following a meal. All data within these bins  
161 will be pooled across meals for each participant prior to calculating % time <54 mg/dL and %  
162 time <70 mg/dL.

163 Postprandial incremental area under the curve (iAUC) will be calculated using the trapezoidal  
164 method [1]. For each meal the baseline value will be set equal to the most recent CGM glucose  
165 measurement prior to the carb entry. If the most recent measurement occurred more than 15  
166 minutes prior to the carb entry than baseline glucose for that meal will be considered missing and  
167 postprandial iAUC will not be calculated. At least 3 hours of CGM data in the 4-hour  
168 postprandial period must be available to calculate iAUC. For each participant the iAUC  
169 calculated for each meal will be averaged. This will be done separately for the lead-in and  
170 treatment periods.

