### 61 **5.3 Exploratory Endpoints**

62 *CGM Metrics: overall and during daytime, nighttime, and postprandial periods*

- 63 • % time in range 70-180 mg/dL, % time  $>180$  mg/dL, % time  $>250$  mg/dL, and % time in  
64 range 70-140 mg/dL
- 65 • Mean glucose
- 66 • Glycemic coefficient of variation (CV) and glycemic standard deviation (SD)
- 67 • Rate of hyperglycemia events, defined as 90 or more minutes  $>300$  mg/dL within 120  
68 minutes (overall, daytime, and nighttime only)
- 69 • Postprandial incremental area under the glucose curve (postprandial period only)
- 70 • Peak postprandial glucose (postprandial period only)
- 71 • % time  $<54$  mg/dL, % time  $<70$  mg/dL, and rate of hypoglycemic events, defined as 15  
72 or more consecutive minutes  $<54$  mg/dL (daytime and nighttime only)

73 *HbA1c Metrics*

- 74 • HbA1c change from baseline

75 *Insulin Metrics: overall and during daytime, nighttime, and postprandial periods, calculated per*  
76 *day or per meal as appropriate*

- 77 • Average bolus insulin
- 78 • Average manual bolus insulin
- 79 • Average automated bolus insulin
- 80 • Average basal insulin
- 81 • Average total insulin

82 *System Use: overall*

- 83 • % CGM use
- 84 • % Closed loop use
- 85 • % Time in different operational modes

86 *Patient Reported Outcomes*

- 87 • TRIM-Diabetes (TRIM-D)
  - 88 ○ Total Score
  - 89 ○ Treatment Burden Subscale
  - 90 ○ Daily Life Subscale
  - 91 ○ Diabetes Management Subscale
  - 92 ○ Compliance Subscale
  - 93 ○ Psychological Health Subscale
- 94 • Trim-Diabetes Device (TRIM-DD)
  - 95 ○ Total Score
  - 96 ○ Device Function Subscale
  - 97 ○ Device Bother Subscale
- 98 • Insulin Treatment Satisfaction Question (ITSQ)
  - 99 ○ Total Score
  - 100 ○ Inconvenience Subscale
  - 101 ○ Lifestyle Subscale
  - 102 ○ Hypoglycemic Control Subscale
  - 103 ○ Glycemic Control Subscale
  - 104 ○ Delivery System Subscale

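### Read literally, SAP 6.2.1 makes the exploratory endpoint peak postprandial glucose one maximum over about 42 lead-in meals versus about 255 treatment meals, which biases the comparison against Lyumjev

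*SAP*

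**What the plan says.** SAP 5.3 lists peak postprandial glucose among the exploratory CGM metrics and gives no formula. SAP 6.2.1 sets the general rule: all postprandial CGM "data will be pooled for each participant when calculating CGM metrics, and metrics will be" derived separately for lead-in and treatment. One metric has a different rule. The iAUC "calculated for each meal will be averaged. This will be done separately for the lead-in and" treatment periods, and it needs at least 3 of the 4 hours of data. No such sentence is written for peak glucose.

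The two periods differ in length. Under SAP 6.2, lead-in metrics are obtained "by pooling all CGM data collected in the last 16 days of the lead in period", while data "from the start of the treatment period until the date of the 13-week visit will be used to calculate" the treatment-period metrics. Days with a meal or exercise challenge, and the nights after them, are left out of both. SAP 6.2.1 adds: "Meals are defined as the 3 largest carb entries on a calendar day".

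SAP 8.3 tests lead-in against treatment for all exploratory CGM endpoints, postprandial ones included, with a linear mixed model, a 95% confidence interval and a two-sided p-value. No step equalises the length of the periods or the number of meals.

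**The concern.** Pooling does no harm to a mean or a percentage of time, because the expected value of neither depends on how many meals are pooled. A maximum is different: the more meals are observed, the higher the largest reading is expected to be. If peak is taken from the pooled data, the longer Lyumjev period gives a higher value even when the two insulins act identically.

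Protocol 1.2 says that a faster insulin may lessen glucose excursions, especially after meals. Peak glucose after everyday meals bears directly on that idea, and the bias works against it. A true reduction could be hidden or reported as a rise. The p-value also belongs to the false-discovery-rate group in SAP 13 that holds HbA1c and the other lead-in versus treatment CGM outcomes. A rejection built in by the derivation can therefore affect the adjusted results of other endpoints.

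**Working it through.** The plan gives no figure for this endpoint, and SAP 4 says that the 160 completers do not come from a statistical calculation, so there is nothing to reproduce. The check asks what a pooled maximum would show if nothing changed.

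**Number of meals**
- Lead-in: 16 days (SAP 6.2) minus 2 challenge days (SAP 6.2.3; Protocol 5.1 puts challenges at least 48 hours apart, so they fall on separate days) = 14 days. At 3 meals a day, 14 × 3 = 42.
- Treatment: 91 days minus 6 challenge days = 85 days, and 85 × 3 = 255.
- Ratio: 255 / 42 = 6.1.

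**Expected maximum.** For n independent standard normal meal peaks, E[max] = ∫ x · n · φ(x) · Φ(x)^(n−1) dx.
- n = 42: 2.18 SD above the mean, with SD of the maximum 0.475.
- n = 255: 2.83 SD above the mean, with SD of the maximum 0.392.
- Null shift: 0.645, or about 0.65 within-person SD, higher on treatment.
- Without the challenge-day exclusions (48 versus 273 meals): 0.61 SD.

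**Standard errors.** The SD of the within-participant difference is √(0.475² + 0.392²) = 0.616 SD. With 160 participants the standard error is 0.616 / √160 = 0.049 SD, so the shift is 0.645 / 0.0487 = 13 standard errors, whatever the SD in mg/dL. If only half the treatment meals are usable (42 versus 127), it is still about 8.

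**Share of participants.** With exchangeable days and no ties, the treatment maximum is the higher one with probability 85 / (14 + 85) = 86%.

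**In mg/dL.** The documents give no SD, mean peak, distribution or sensor ceiling, so all of these are assumed:

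| Assumed meal peaks | Null shift (mg/dL) |
|---|---|
| Normal, SD 30 / 45 / 60 | 19 / 29 / 39 |
| Normal, SD 45, within-day correlation 0.3 to 0.5 | 30 to 31 |
| Lognormal, mean 190, SD 45, no ceiling | 50 |
| Normal, mean 220, SD 60, ceiling 400 | 32 |
| Lognormal, mean 250, SD 60, ceiling 400 | 17 |
| Normal, mean 270, SD 60, ceiling 400 | 13 |

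The mean peak is 190 where the table does not give one, and it does not affect the uncapped normal rows. Each row comes from simulating 160 participants under no change, with a between-person SD of 25 mg/dL. A paired test at the 5% level rejected in every replicate. An unpaired test, run on every row but the last, did so too. T-tests stood in for the SAP's mixed model. The range is illustrative and not a bound: a higher mean against a ceiling gives less than 13, and a more strongly skewed shape without a ceiling gives more than 50.

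**Peak per meal, then averaged.** With the same simulated data (SD 45, 1000 replicates), the null difference was −0.02 mg/dL and the rejection rate 5.4%. In the other scenarios run with this rule (200 replicates each), the difference stayed within 0.1 mg/dL and rejection was 2.5% to 7.5%.

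**The case against.** The strongest reply is that the SAP never states how peak is derived. Its 4-hour window is set meal by meal, which also suits a per-meal peak. The sentence that spells out pooling across meals concerns the percentages of time below 54 and 70 mg/dL. iAUC may have its own paragraph only because it needs a baseline and a trapezoid rule. This stands in part: a reader might infer that the authors intend a period-wide maximum, and the documents do not show that intent. They do contain a general pooling rule that covers CGM metrics, with one written exception, and SAP 6.2 sets the postprandial data minimum at 24 hours for the whole period. A programmer who follows the text would produce one maximum per participant and period.

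A reader might also infer that the trial's conclusion, or its evidence on meals in general, is compromised. The documents do not support that. Peak is exploratory, and the success rule rests on severe hypoglycemia and DKA. Postprandial time in ranges and mean glucose, as well as iAUC, are not shifted by period length. SAP 6.2.3 takes the meal-challenge peak in fixed windows, and SAP 8.4 compares the no-bolus challenge between periods. Protocol 5.1.1 has each participant eat the same meal, so a like-for-like peak comparison is already planned.

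It is also fair that the mg/dL sizes rest on assumed inputs, and that early dropouts contribute fewer treatment meals, so their bias is smaller or even reversed.

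**Conclusion.** The point holds for peak glucose after everyday meals. Followed as written, the SAP compares maxima over about 42 and about 255 meals, and with no true change the result favours Humalog by about 0.65 within-person SD, or 13 standard errors at n = 160. That figure assumes three usable meals a day, full follow-up, and independent, normally distributed meal peaks with the same distribution in both periods. The direction also held with within-day correlation, skewed peaks, fewer usable treatment meals and an assumed 400 mg/dL ceiling. The size in mg/dL, roughly 13 to 50, is illustrative.

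This should be fixed because a general rule in the SAP gives a misleading test and the repair is trivial. It is not a must-fix: nothing in the key or secondary safety endpoints depends on it.

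**What to change.** Add one sentence to SAP 6.2.1: peak postprandial glucose is the maximum CGM value within each meal's window, averaged over meals within participant and period, and this average is the quantity tested under SAP 8.3.

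Set any minimum amount of data per meal window separately and apply it identically in both periods. The 3-of-4-hour rule for iAUC is one option, but SAP 6.2.1 ends a window at the next carb entry, so that rule would drop meals followed by another entry within 3 hours.

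The cost is a sentence and a small programming change, with no new data. The SAP version table records follow-up as complete at version 4.0, so the date of the change and the reason for it should be documented. If per-meal averaging was intended all along, the same sentence settles it.
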